13.4 Assessment of respiratory rate and oxygen saturation

To assess the respiration of the patient, peripheral capillary oxyhemoglobin saturation (SpO₂) will be repeatedly reported (Table 3). Respiration rate will be assessed according to hospital staff's current clinical practice.

14 Pharmacokinetics, disease markers, and biomarkers

All laboratory samples for IMU-838 plasma trough levels, disease markers and biomarkers must be handled and labeled according to the respective laboratory manual i.e., virologic samples according to the manual from the central virology laboratory, all other samples according to the central safety laboratory manual.

14.1 Plasma trough levels of IMU-838

IMU-838 plasma trough level concentrations will be determined by validated direct liquid chromatography tandem-mass spectrometry. This method determines the concentration of the active moiety vidofludimus contained in IMU-838. Details of the assay will be described in a separate bioanalytical report.

Plasma samples for IMU-838 trough levels will be assessed centrally at Nuvisan. Samples will be collected and subsequently stored at at least -20°C (-4°F) at the site, and shipped to the central laboratory as frozen samples, as appropriate. Investigators will be provided with detailed written instructions how to collect, handle, store, and ship the samples.

Blood samples to assess IMU-838 serum trough values will be collected in all patients as specified in the schedule of assessments in the morning before the first IMP dose (Table 3).

Patients are required to withhold intake of the IMP until after the blood sample collection. Plasma trough will be assessed using Lab Kit PK.

14.2 Disease markers

The following blood biomarkers will be evaluated:

- D-dimer
- LDH
- CRP
- cTn
- PCT

Disease markers are part of Lab Kit B, must be frozen at at least -20°C (-4°F) and sent within 6 weeks (for more details on lab kits see also [Appendix 1](#)).

14.3 Biomarkers

The following biomarkers will be evaluated (in blood samples if not indicated otherwise):

- Serial viral load assessed by RT-PCR in spontaneous sputum and nasopharyngeal swab (samples must be frozen at at least -20°C [-4°F] and sent within 7 days, Lab Kit D)*
- Qualitative virus assessment: SARS-CoV-2 status (qualitative) in sputum and nasopharyngeal swab as derived from the viral load assessment (i.e. may be evaluated as absence or presence of virus in the quantitative SARS-CoV-2 RT-PCR assessments)
- Biomarkers: IL-17, IL-1 β , IL-6, IFN γ , and TNF α (assessed with Lab Kit C, samples must be frozen at at least -20°C [-4°F] and sent within 6 weeks)
- Serology: IgA and IgG antibodies against SARS-CoV-2 (Lab Kit E, samples must be frozen at at least -20°C [-4°F] and sent within 6 weeks)

For more details on lab kits, storage and shipment conditions see [Appendix 1](#).

For the sputum sample, no induced sputum should be attempted. If spontaneous sputum cannot be obtained, this should be noted and no sample needs to be sent.

* At each time point indicated in [Table 3](#) only 1 nasopharyngeal swab and 1 sputum sample will be taken. The results of the viral load test will also be used for the qualitative assessment.

For centers in the USA: 2 additional blood samples as indicated in [Table 3](#) will be collected to evaluate immune cells and immune reactions for future research studies. Shipment needs to be done at ambient temperature and immediately the same day after sampling. Samples will be shipped directly to a US research site and not to the central laboratory. This blood collection is optional and only for patients agreeing to the extra biomarker assessment on the ICF.

15 Safety assessments

15.1 Adverse events documentation and reporting

15.1.1 Definitions

15.1.1.1 Adverse events

An AE is any untoward medical occurrence in a patient or clinical investigation subject administered a pharmaceutical product, which does not necessarily have a causal relationship with this treatment. An AE can therefore be any unfavorable and unintended sign (including an abnormal laboratory finding), symptom, or disease temporally associated with the use of the IMP, whether or not related to the IMP.

Overdosing, defined as intake of more than twice the intended dose, will not be considered an AE but must be documented as protocol deviation. However, symptoms associated with overdose are considered adverse drug reactions (ADR, for definition see below).

Untoward medical experiences occurring during pre-treatment periods do not meet the above-mentioned definition of AE. Nevertheless, they have to be documented in the same way as AEs, if they occur in the safety monitoring period, i.e., between signing the informed consent form and completion of the EoS visit. Should they already be present at Screening and don't worsen later on, they will only be documented as medical history.

A surgery or procedure scheduled to occur during the trial will not be considered an AE if the surgery or procedure will be performed for a pre-existing condition and the surgery or procedure was planned prior to trial entry. However, if the pre-existing condition deteriorates unexpectedly during the trial (e.g., surgery performed earlier than planned), then the deterioration of the condition for which the surgery or procedure is being done will be considered an AE.

Diagnostic medical or non-surgical procedures will not be considered as AEs. Hospital admission for social, quarantine or convenience reasons will also not be recorded as AE.

AEs that occur between signing the informed consent form and the time when the patient first administers the IMP (Day 0) are defined as pre-treatment AEs.

Treatment-emergent adverse events are defined as any event not yet present prior to the first intake of IMP or any event already present that worsens in either intensity or frequency following exposure to the IMP.

A continuous event with changing intensities will be considered as one event of the most severe intensity documented. A continuous event with a changing seriousness will also be considered as one event, but the start and stop date of the time the event is serious must be separately documented. Clearly separated episodes of an event will be considered as separate events.

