15.1.3 Documentation of adverse events

All AEs occurring between the time written informed consent was obtained and until the end of the safety follow-up period (safety observation period) must be recorded. Information on AEs will be derived by non-directive questioning of the patients in general terms at each visit if possible (e.g., "How do you feel?" or "How have you been since the last questioning?"), by patients' spontaneous reports, or by observation. Adverse events also may be detected when they are volunteered by the patient during or between assessments and/or visits or through physical examination, laboratory test, or other assessments.

* Instrumental ADL refer to preparing meals, shopping for groceries or clothes, using the telephone, managing money, etc.

** Self care ADL refer to bathing, dressing and undressing, feeding self, using the toilet, taking medications, and not bedridden.

All AEs that occur during the safety observation period of the trial as described above will be recorded in the patient's AE section of the eCRF and will include the following information: a description of the AE, date of onset and resolution, severity, relationship to the IMP, relationship to trial procedure, action taken, and outcome. For SAEs, the SAE form must be completed (see Section 15.1.4).

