15.1.6 Handling of anticipated clinical events of COVID-19

Typical COVID-19-related symptoms present at Baseline (examples such as fever, dyspnea, viral pneumonia, or hypoxia) and continuing during the trial without clinically unusual worsening* are considered anticipated clinical events of the underlying condition and will not be collected as AEs. In addition, disease characteristics and severity will be regularly captured within the scope of the clinical status assessment. Death, hospitalization, and use of ventilation, ECMO, or dialysis due to COVID-19 or its complications (which all are recorded as clinical endpoints for this trial) are not considered AEs (see Section 15.1.2) and should not be considered medically significant events by itself for the assessment of SAEs.

Any clinically unusual worsening* of COVID-19-related disease symptoms present at trial inclusion and any clinically relevant changes in clinical laboratory parameters, vital signs or other findings during physical examination which are considered unusual for COVID-19 disease and where a relationship to drug treatment cannot be excluded should be recorded as AEs.

* “Unusual worsening” means that, in terms of type or severity of symptoms, time frame or symptom fluctuations, the course of the disease progression is different from that in most patients with the same general conditions (disease status, age, health status, concurrent diseases).

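### A continuous AE that starts before the first dose keeps one onset date and its worst grade, so later worsening in intensity cannot be identified; the onset date of an unusual-worsening AE is also unstated

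*Combined protocol and SAP*

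**What the plan says.** Section 15.1.1.1 sorts AEs by timing. Those that start after consent and before the first intake "are defined as pre-treatment AEs". Treatment-emergent AEs (TEAEs) are events not present before the first intake, together with "any event already present that worsens in either intensity or frequency following exposure to the IMP".

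The same section then says how a changing event is recorded:

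- Changing intensity: "A continuous event with changing intensities will be considered as one event of the most severe intensity documented".
- Changing seriousness: also one event, "but the start and stop date of the time the event is serious must be separately documented".
- Recurrence: "Clearly separated episodes of an event will be considered as separate events".

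Section 15.1.3 lists the content of each AE record: "a description of the AE, date of onset and resolution, severity, relationship to the IMP, relationship to trial procedure, action taken, and outcome".

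Under Section 15.1.6, COVID-19 symptoms present at baseline that run on without unusual worsening are not AEs. Sites are asked to record as an AE any clinically unusual worsening "of COVID-19-related disease symptoms present at trial inclusion". The section gives no rule for the onset date of such an AE.

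**The concern.** The worsening part of the TEAE definition needs two facts: the intensity at first dose, and whether a higher intensity was reached later. The recording rule for intensity keeps neither. It keeps the maximum over the whole event, attached to a single onset date. The paragraph does ask for dates when seriousness changes, so the omission concerns intensity only, and intensity is what the TEAE definition depends on.

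An analyst facing such a record has two choices, and each goes wrong in its own way. If TEAE status is taken from the onset date, an event that truly worsened on treatment is left out. If every AE that was ongoing at first dose is counted as treatment-emergent, severity reached before dosing is charged to treatment. The lost information is hard to rebuild after the fact, because it was never entered.

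The silence in 15.1.6 creates a related risk. With about 10 to 45 centers planned (Section 6), some sites could date an unusual-worsening AE from the worsening and others from the start of the symptom. The second choice would move the event into the ambiguous class.

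**Working it through.** No figure in the plan bears on this point, so there is nothing to reproduce. The check asks, for each type of event, whether the fields in 15.1.3, recorded under the rules of 15.1.1.1, are enough to apply the TEAE definition.

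**Two contrasting events, both starting after consent and before the first dose, both continuous, neither changing seriousness.**

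| | Event A | Event B |
|---|---|---|
| Before first dose | Grade 1 | Grade 3 |
| After first dose | Grade 3 on Day 5 | Grade 1 |
| Recorded onset | before first dose | before first dose |
| Recorded severity | Grade 3 | Grade 3 |
| TEAE under 15.1.1.1? | yes, worsened | no |

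The timing and severity fields are identical, yet the definition puts the two events in different classes. No section asks for the grade at first dose, the date of a grade change, or a flag for worsening after dosing.

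**Derivability by type of event.**

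1. Onset after first intake: treatment-emergent by the first part of the definition. Derivable.
2. Onset between consent and first intake, continuous, intensity rising after dosing: not derivable from the listed fields, as the table shows. If the event also becomes serious after dosing, the start of the serious period is dated and the change can be seen.
3. Clearly separated episodes: each is its own record with its own dates and grade, so worsening in frequency can be derived.
4. A condition or COVID-19 symptom present at Screening that worsens after dosing: the baseline state is medical history (15.1.1.1) or an anticipated event (15.1.6), with no AE record. If the AE is dated from the worsening, it falls under type 1 and is derivable. If a site enters the start of the symptom, the AE has a pre-dose onset and cannot be classified by date. The text does not settle which.

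**Size of the window for type 2.** Section 8.1 allows screening from Day -2 to Day 0, and Section 11.1.5 allows the first dose as late as 02:00 on Day 1. The longest possible span, from 00:00 on Day -2, is 24 + 24 + 24 + 2 = 74 hours. Sections 8.1 and 12.2 encourage screening, randomization and first dose on the same day, so the usual window is much shorter.

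**The case against.** The case against making much of this is strong on scope.

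A reader might infer that every unusual-worsening AE carries a pre-dose onset, which would make the gap large. The documents do not support that. Section 15.1.6 does not collect baseline COVID-19 symptoms as AEs, so there is no earlier record for the one-event rule to merge with. What it asks for is the worsening itself. Section 15.1.1.1 treats a pre-existing condition that deteriorates and brings planned surgery forward in the same way: the deterioration is the AE. Dating from the worsening is the natural reading. The fault is only that it is not written down.

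A reader might also infer that the whole worsening limb is unusable. It is not. Separate episodes serve the frequency part, and a change to serious is dated. Where CTCAE has no specific grading, Section 15.1.2 defines Grades 3 and 4 in terms that overlap the seriousness criteria in 15.1.1.3, so some of the higher-grade worsening would be dated by that route.

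Nor can the dilution of a between-arm safety comparison be sized. The documents give no share of AEs in the affected class. If the same share were lost in both arms, the absolute difference would shrink but the risk ratio would not. Part 1 plans no formal tests (16.3.1).

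Three further points stand. The safety stopping criteria in Section 20.1 count SAEs by grade and ignore TEAE status. Worsening of COVID-19 is also captured during inpatient treatment through the daily WHO score and twice-daily SpO2, vital signs and oxygen support (Table 3). The list in 15.1.3 says what a record will include and does not exclude more; the eCRF could hold a grade history, and 16.3.1 defers analysis detail to a statistical analysis plan. The text available contains neither an eCRF specification nor a TEAE derivation.

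None of this supplies the missing grade for type 2 events. A later analysis plan cannot derive what the recording rule told sites not to keep.

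**Conclusion.** The point holds in a narrow form and is minor. For a continuous AE that begins between consent and first intake and does not change seriousness, the recording rule and the listed fields do not separate worsening after dosing from severity before it, although the TEAE definition requires that separation. Section 15.1.6 separately leaves the onset date of unusual-worsening AEs unstated.

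The affected class is bounded by a window of at most about 74 hours per patient. Its frequency is unknown, and the documents give no basis for estimating an effect on safety tables. The safety stopping criteria are not touched. The conclusion assumes that the eCRF holds the fields listed in 15.1.3 and no log of grade changes. If such a log exists, only the onset rule in 15.1.6 remains to be clarified.

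**What to change.** In Section 15.1.1.1, limit the one-event rule to events that start after the first intake. Add that an event present before the first intake which worsens in intensity or frequency afterwards is closed on the day it worsens and entered as a new AE with its own onset date and grade. An equivalent is to keep one record but add the grade at first dose and the date of the first post-dose increase, as is already done for seriousness.

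In Section 15.1.6, state that the onset of an unusual-worsening AE is the date of the worsening.

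In the statistical analysis plan, derive TEAE status and TEAE grade from that date.

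The cost is a sentence or two in the protocol, a matching line in the eCRF completion guidance, and a few more AE records. Nothing changes for patients.

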15.1.1.2 Adverse drug reactions and unexpected adverse drug reactions

All AEs judged by either the reporting investigator and/or the Sponsor as having a reasonable causal relationship to the IMP qualify as ADR. The expression reasonable causal relationship means to convey in general that there is evidence or argument to suggest a causal relationship.

An unexpected ADR is an adverse reaction, the nature or severity of which is not consistent with the applicable product information (e.g., investigator's brochure for an unapproved investigational product or package insert or summary of product characteristics for an approved product). Reports that add significant information on specificity or severity of a known, already documented AE constitute unexpected AEs, too. For example, an event more specific or more severe than described in the reference document would be considered 'unexpected'. Specific examples would be: acute renal failure as a labeled AE with a subsequent new report of interstitial nephritis or hepatitis with a subsequent report of autoimmune hepatitis.

15.1.1.3 Serious adverse events

An SAE is any untoward medical occurrence that, at any dose:

- results in death
- is life-threatening
- requires inpatient hospitalization or prolongation of existing hospitalization
- results in persistent or significant disability or incapacity
- results in a congenital abnormality or birth defect

NOTE: The term "life-threatening" in the definition of "serious" refers to an event in which the patient was at risk of death at the time of the event; it does not refer to an event, which hypothetically might have caused death, if it were more severe.

Medical and scientific judgment will be exercised in deciding whether expedited reporting is appropriate in other situations, such as important medical events that may not be immediately life-threatening or result in death or hospitalization, but may jeopardize the patient or may require intervention to prevent one of the other outcomes listed in the definition above. These will usually also be considered serious.

Examples of such events are intensive treatment in an emergency room or at home for allergic bronchospasm; blood dyscrasias or convulsions that do not result in hospitalization; or development of drug dependency or drug abuse. In addition, new malignancies that occur during the participation in the trial are defined as important medical events and must be reported as SAEs.

An SAE requires that the underlying event is considered an AE as defined in Section [15.1.1.1](#).

Hospitalizations due to a surgery or procedure during the trial will not be considered an SAE if the surgery or procedure will be performed for a pre-existing condition and the surgery or procedure was planned prior to trial entry. However, if the pre-existing condition deteriorates unexpectedly during the trial (e.g., surgery performed earlier than planned), then the deterioration of the condition leading to hospitalization will be considered an SAE. Hospital admission for social, quarantine, or convenience reasons will not be recorded as SAE. Hospitalization and death due to COVID-19 are anticipated clinical events of the underlying disease and cannot be used as reason for SAE classification without an underlying AE leading to hospitalization or death (see also Section 15.1.6).

15.1.1.4 Suspected unexpected serious adverse reaction

A **suspected unexpected serious adverse reaction (SUSAR)** is a serious adverse reaction (SAR) that is unexpected or for which the development is uncommonly (unexpected issue) observed during a clinical trial and for which there is at least a reasonable possibility of a causal relationship with the IMP.

15.1.2 Classification of adverse events

Classification of AEs will be performed by the investigator.

Causality

The causal relationship between the AE and the administration of the IMP or trial procedure will be assessed as follows:

- Related: Implies a reasonable possibility of a causal relationship between the event and the IMP or procedure. This means that there are facts (evidence) or arguments to suggest a causal relationship.
- Not related: Implies no reasonable possibility of a causal relationship between the event and the IMP or procedure. This means that there are neither facts (evidence) nor arguments to suggest a causal relationship.

Severity

The severity of AEs will be graded according to the National (US) Cancer Institute-Common Terminology Criteria for Adverse Events (NCI-CTCAE), Version 5.0. If not specifically defined in the NCI-CTCAE, the following grading applies:

Grade 1: mild; asymptomatic or mild symptoms; clinical or diagnostic observations only; intervention not indicated

Grade 2: moderate; minimal, local or noninvasive intervention indicated; limiting age-appropriate instrumental activities of daily living (ADL)*

Grade 3: severe or medically significant but not immediately life-threatening; hospitalization or prolongation of hospitalization indicated; disabling; limiting self-care ADL **

Grade 4: Life-threatening consequences; urgent intervention indicated

Grade 5: Death related to AE

Outcome categories

Recovered: The patient has fully recovered from the event or the condition has returned to the level observed at Baseline

Recovering: The patient has recovered from the event, but the condition has not returned to the level observed at Baseline

Not recovered: The event is ongoing at the time of reporting and the patient has still not recovered

Recovered with sequelae: As a result of the AE, the patient suffered persistent and significant disability/incapacity (e.g., became blind, deaf or paralyzed)

Fatal: The patient died due to the event. If the patient died due to other circumstances than the event, the outcome should be stated otherwise (e.g., not recovered or recovering)

Unknown: If the outcome is not known or not reported

15.1.3 Documentation of adverse events

All AEs occurring between the time written informed consent was obtained and until the end of the safety follow-up period (safety observation period) must be recorded. Information on AEs will be derived by non-directive questioning of the patients in general terms at each visit if possible (e.g., "How do you feel?" or "How have you been since the last questioning?"), by patients' spontaneous reports, or by observation. Adverse events also may be detected when they are volunteered by the patient during or between assessments and/or visits or through physical examination, laboratory test, or other assessments.

* Instrumental ADL refer to preparing meals, shopping for groceries or clothes, using the telephone, managing money, etc.

** Self care ADL refer to bathing, dressing and undressing, feeding self, using the toilet, taking medications, and not bedridden.

All AEs that occur during the safety observation period of the trial as described above will be recorded in the patient's AE section of the eCRF and will include the following information: a description of the AE, date of onset and resolution, severity, relationship to the IMP, relationship to trial procedure, action taken, and outcome. For SAEs, the SAE form must be completed (see Section 15.1.4).

